We will conduct an 8-week, non-randomized, open label study of brexpiprazole in 20 persons with bipolar disorder. Primary Aim will be to determine if brexpiprazole is associated with a reduction in depressive symptom severity using the Montgomery-Asberg Depression Rating Scale (MADRS) in outpatients with bipolar disorder, depressed mood state. Secondary Aims will be: 1) Assess manic symptoms in patients with bipolar disorder receiving brexpiprazole, 2) Assess cognition in patients with bipolar disorder receiving brexpiprazole, 3) Assess the safety and tolerability of brexpiprazole in patients with bipolar disorder, 4) Assess quality of life in patients with bipolar disorder receiving brexpiprazole.

Subjects will be discontinued from the study if any of the following conditions occurs: change in diagnosis to other than bipolar I or II disorder, development of active suicidal or homicidal ideation with plan and intent, worsening in mood symptoms, that in the opinion of the investigators requires discontinuation, pregnancy, development of severe or life-threatening medical condition, involuntary psychiatric hospitalization or incarceration.

4. Study Procedures:

Baseline: This visit will be split into two portions: Baseline 1 and Baseline 2.

For Baseline 1 (~3 hours), the psychiatric diagnosis will be confirmed by the structured clinical interview for DSM-5 (SCID), mood assessed via the Montgomery-Asberg Depression Rating Scale (MADRS), depression via the Inventory of Depressive Symptomatology Self-Report (IDS-SR₃₀), mania via the Young Mania Rating Scale, and quality of life via the Quality of Life in Bipolar Disorder (QOLBD). Blood will be drawn for complete blood count (CBC), Comprehensive Metabolic Panel (CMP, includes a liver panel with AST, ALT, as well as lipids), and high-sensitivity c-reactive protein (hs-CRP). A urine sample for drug screen and pregnancy test (if applicable), psychiatrist assessment, physical exam, collection of weight and vitals will be completed.

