For Baseline 2 (~2 hours), recent depressive symptoms will be assessed via the IDS-SR₃₀ and MADRS, mania via the YMRS, current mood via Internal State Scale (ISS), suicidal ideation will be assessed via the Columbia Suicide Severity Rating Scale (CSSRS), safety and side effects will be assessed with the SAFTEE, the Abnormal Involuntary Movement Scale (AIMS), Barnes Akathisia Scale (BAS) and Simpson-Angus Scale (SAS). Subjects will also complete the The Ray Auditory Verbal Learning Test (RAVLT) to assess word memory, the Stroop test to measure attention, speed, and accuracy of thinking, and The Trail Making Test (TMT) to measure attention, speed and accuracy. A urine sample for drug screen and pregnancy test (if applicable) will also be completed. Brepiprazole capsules will be initiated at 0.5 mg/day.

Baseline 2 to Week 1: Subjects will be given the ISS to fill out at home. Subjects will be asked to complete the scale at home on 7 consecutive days between Baseline 2 and Week 1 visits and return the filled out scales to the researcher's office. The scale will take approximately 3-5 minutes to fill out.

Week 1, 2, 3, 6 (~1.5 hours each): Subjects will complete the MADRS, YMRS, IDS-SR₃₀, ISS, SAFTEE, CSSRS, AIMS, BAS, SAS, and a urine sample will be collected for a drug screen. Subjects will meet with the psychiatrist for weekly assessment and vitals will be collected.

Week 4 (~2 hours): Subjects will complete the MADRS, IDS-SR, YMRS, SAFTEE, ISS, C-SSRS, AIMS, BAS, SAS, RAVLT, Stroop, TMT, vital signs, a urine sample for a drug screen and a urine pregnancy test, and visit the doctor for a psychiatric evaluation.

Week 8 (final visit ~2.5 hours): Subjects will complete the MADRS, IDS-SR, YMRS, SAFTEE, ISS, C-SSRS, AIMS, BAS, SAS, RAVLT, Stroop, TMT, QOLBD, vital signs, a urine sample for drug screen, take a urine pregnancy test, have blood drawn for clinical testing (CBC, CMP, hs-CRP), and visit the doctor for a psychiatric evaluation and physical exam. During this visit, participants will also

be provided with aftercare referral information and will begin their medication taper. The medication taper schedule is described below under “Study Medication and Intervention Description”.

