Safety Phone Call (~15 min): Participants will receive a phone call from researchers 7-10 days following their Week 8 study visit (at the end of their tapering schedule). During this phone call, the researchers will assess any withdrawal effects or adverse events and check on the status of the aftercare referrals.

Participants will be paid for their time and inconvenience per visit as follows: \$60 at Baseline 1, Baseline 2, weeks 1, 2, 3, 6; \$70 at week 4; \$90 for week 8. Participants will also be paid for each ISS scale they bring back at the rate of \$1 per scale (maximum \$7). These payments will be processed during Week 1 visit. These payments will be completed via the ClinCard system. Bus or rail passes will be provided. After study completion, standard psychiatric care will be provided until referral is arranged.

Study Medication and Intervention Description:

Participants will be initiated on a 0.5 mg/day brexpiprazole dose (week 0/baseline); after one week the dose will be increased to 1 mg/day (week 1), after another week to 2 mg/day (week 2). If any dose appears to be poorly tolerated, the dose titration can be slowed or stopped based on clinician judgment. If response in weeks 3-6, defined as a 50% reduction in the MADRS, has not been achieved, and the current dose is well tolerated, then additional dose increases to 3 mg/day and 4 mg/day (maximum allowed dose in protocol) will occur with at least a one week interval between dose increases.

Following the last study visit (Week 8), participants will be gradually tapered off the medication every 2 days until they stop taking the medication completely. For example, if a participant takes 4 mg of brexpiprazole at Week 8, then he/she will take 3 mg for 2 days, then 2 mg for 2 days, then 1 mg for 2 days, and then 0.5 mg for 2 days. At the end of the tapering period (7-10 days depending on the highest brexpiprazole dose at the end of the study), participants will receive a safety phone call from a research staff member to assess any withdrawal symptoms and check on the status of the aftercare referrals.

5. Sub-Study Procedures:

No sub-study procedures are anticipated at this time.

6. Criteria for Inclusion of Subjects:

- Outpatient men and women ages 18-65
- Bipolar I or II disorders, currently depressed mood state based on a SCID for DSM-5; Mixed features in DSM-5 are allowed, but those with a Young Mania Rating Scale score ≥ 15 will be excluded
- MADRS score ≥ 25 at baseline 2 visit.

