7. Criteria for Exclusion of Subjects:

- Mood disorders other than bipolar I or II disorders (e.g., bipolar NOS, or cyclothymic disorders, schizophrenia, schizoaffective disorder, or unipolar depression based on the SCID), other disorders, e.g. anxiety disorders, will be allowed
- Current (last 14 days) treatment with an antipsychotic or antidepressant. If a participant has been treated with any antipsychotic or antidepressant in the last 14 days, then they will not be enrolled in the study. No washout of antipsychotic or antidepressant will be done
- History of neuroleptic malignant syndrome or tardive dyskinesia
- Prior history of brexpiprazole use
- Vulnerable populations (e.g., pregnant, nursing, cognitively impaired, incarcerated)

- High risk for suicide defined as > 1 attempt in past 12 months that required medical attention, any attempt in the past 3 months or current suicidal ideation with plan and intent such that outpatient care is precluded
- Severe or life-threatening medical condition, or laboratory or physical examination findings consistent with serious medical illness (e.g., dangerously abnormal electrolytes)
- Moderate or severe hepatic or renal impairment based on medical history and laboratory analyses
- Taking moderate or strong inducers or inhibitors of CYP2D6 or CYP3A4

8. Sources of Research Material:

Clinical information will be obtained via the Structured Clinical Interview for DSM (SCID), Montgomery-Asberg Depression Rating Scale (MADRS), Inventory of Depressive Symptomatology—Self-Report 30-item version (IDS-SR₃₀), Young Mania Rating Scale (YMRS), Columbia Suicide Severity Rating Scale (C-SSRS), Systematic Assessment for Treatment Emergent Effects (SAFTEE), Abnormal Involuntary Movement Scale (AIMS), Barnes Akathisia Scale (BAS), Simpson-Angus Scale (SAS), Ray Auditory Verbal Learning Test (RAVLT), The Stroop and Trail Making Test (TMT).

Biological information will be obtained via blood drawn (2 tbsps ~ 29mLs) for laboratory analyses including a complete blood count (CBC) and Comprehensive Metabolic Panel (CMP, includes a liver panel with AST, ALT, as well as lipids), high-sensitivity c-reactive protein (hs-CRP). A redraw may be requested if the first sample cannot be processed. A physical examination will be performed, weight obtained, and a urine sample collected for a drug screen and pregnancy testing.

9. Recruitment Methods and Consenting Process:

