There are also certain medications that may have clinically significant interactions with brexpiprazole. These medications are moderate or strong inducers or inhibitors of CYP3A4 or CYP2D6. Examples of these medications include, but are not limited to, paroxetine, fluoxetine, quinidine, many HIV medications, etc. A full list of these medications will be made available to participants. This list will also be attached in the IRB application. Participants who currently take moderate or strong inducers or inhibitors of CYP3A4 or CYP2D6 will be excluded from the study. If participants start taking moderate or strong inducers or inhibitors of CYP3A4 or CYP2D6 during their study participation, they will be discontinued from the study and appropriate aftercare referral information will be provided.

Participants will be instructed to let the researchers know of any prescription medications, over-the-counter medications, vitamins and herbal supplements they are currently taking or of ANY new medications they may start taking during their study participation.

Participants will also be informed of potential interaction brexpiprazole may have with alcohol.

Psychological Stress

Some of the questions we will ask you as part of this study may make you feel uncomfortable. You may refuse to answer any of the questions, take a break or stop your participation in this study at any time.

Loss of Confidentiality

Any time information is collected; there is a potential risk for loss of confidentiality. Every effort will be made to keep your information confidential; however, this cannot be guaranteed.

Risks to Sperm, Embryo, Fetus or Breast-fed Infant

Males: Being in this research may damage sperm, which could cause harm to a child that a participant may father while on this study. Subjects who participate in this study and are sexually active, must agree to use a medically-acceptable form of birth control. Medically-acceptable forms of birth control include:

- (1) surgical sterilization (vasectomy), or
- (2) a condom used with a spermicide (a substance that kills sperm).

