The likely risks from the study are primarily medication side effects and the risk of untreated bipolar disorder and depressive symptoms. Brexpiprazole is reasonably well tolerated and may have metabolic side effects than most other atypical antipsychotics. All participants will receive active medication (brexpiprazole) during the study, as well as frequent monitoring and follow-up appointments with a psychiatrist and research coordinator. Thus, all participants will receive care for mood symptoms. At the end of study, patients will be given follow-up appointments at treatment facilities we have worked with in the past, and, if needed, we will provide a longer period of aftercare until treatment can be transitioned to another provider. These are our standard procedures for research studies and have been in place for over 17 years. Another potential risk is worsening of mood symptoms. If participants have a worsening of mood symptoms, such as active suicidal ideation, study participation will be discontinued, and we will provide them with referrals for appropriate care. Some level of suicidal ideation is common in the participants we research. However, we want to take steps to prevent risk of suicidal acts. Thus, the emergence of intense suicidal thoughts with a clear plan (e.g. overdose) and the intent to act on the plan would require discontinuation from the study. However, recurrent suicidal thoughts accompanied by a clear

understanding that the participant does not plan to act on these thoughts would not require discontinuation.

Potential pharmacokinetic or pharmacodynamic drug-drug interactions will be managed using inclusion, exclusion, and discontinuation criteria and dose adjustments. Clinical assessments are collected by trained and experienced staff members who will be able to reassure participants if they are distressed during study visits. If participants become fatigued or stressed during the testing, rest periods will be provided. Standard, appropriate measures will be used to minimize risk of infection during venipuncture.

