All investigators and research staff will be available 24 hours a day. The consent form will have both daytime and nighttime numbers for reaching study personnel. Business cards for the research coordinator and psychiatrists will also be provided. In the event an investigator or research coordinator is on vacation or out-of-town, coverage will be provided, and both the research coordinator and UT Southwestern answering service are informed of the name and pager number of the physician-on-call. In the event of a medical or psychiatric emergency, appropriate medical advice will be provided including recommendations for emergency room evaluation if necessary. The PI and other physicians involved with the study have staff privileges at the Parkland and William P. Clements University Hospital Emergency Rooms, which are likely to be the most commonly used hospitals by the participants. The physicians and other staff have extensive experience working with patients with bipolar disorder and substance use disorders.

All women of childbearing potential (premenopausal and without a clearly documented hysterectomy, ovariectomy or bilateral tubal ligation) must have a urine pregnancy test with negative results prior to receiving study medication. These participants will also be asked to use effective forms of contraception during the study. Pregnancy or failure to use contraceptives will result in discontinuation from the study.

These are general guidelines. In all cases, physician judgment will be used to determine whether or not a participant can safely remain in the study.

12. Procedures to Maintain Confidentiality:

Blood specimens will be provided to Quest Diagnostics for analysis, removing identifying information (e.g., name) that could be linked to the patient's identity prior to sending for analysis. The blood provided to Quest will have the participant's date of birth to correctly link the results to the participant. The results of this test will be de-identified and added to the rest of the de-identified data. Once de-identified, only the identified investigators can learn/discover the names of participant.

Data Management Plan

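### The entry bar on antidepressants and antipsychotics is not carried through week 8, so the benefit of one started on study could be counted as brexpiprazole response or remission

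*Combined protocol and SAP*

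**What the plan says.** - **Entry (Section 7).** Anyone treated with "any antipsychotic or antidepressant in the last 14 days, then they will not be enrolled in the study". The stated consequence is about enrolment; the weeks on study are not mentioned.
- **On study, drugs (Section 10, Study Procedure/Intervention).** "If participants start taking moderate or strong inducers or inhibitors of CYP3A4 or CYP2D6 during their study participation, they will be discontinued", with aftercare referral. Paroxetine and fluoxetine are among the named examples. Participants must report every new medication, but no consequence is attached to drugs outside this group.
- **On study, general (Section 3).** "Subjects will be discontinued from the study if any of the following conditions occurs". The list that follows includes mood worsening that the investigators think calls for it, but no drug. Section 11 also discontinues for worsening mood.
- **Interactions (Section 11).** "Potential pharmacokinetic or pharmacodynamic drug-drug interactions will be managed using inclusion, exclusion, and discontinuation criteria and dose adjustments".
- **Discretion (Section 11).** "In all cases, physician judgment will be used to determine whether or not a participant can safely remain in the study".
- **Analysis (Section 14).** Everyone with one post-baseline assessment is analysed. MADRS and IDS-SR go into a repeated-measures ANCOVA with time as the main effect, and response and remission rates are reported. Nothing is said about scores recorded after another treatment has been added.

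**The concern.** The plan gives drugs that alter brexpiprazole metabolism both an entry exclusion and an on-study rule. Drugs that act on the primary outcome itself get only the entry exclusion. Section 2 names quetiapine and lurasidone as approved for bipolar depression; neither is among the Section 10 examples, and no on-study rule mentions them.

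The study has one arm and no control. If someone who is not improving adds an effective drug and then improves, nothing in the design separates that gain from brexpiprazole. The mean MADRS change and the response and remission rates, which are what a proof-of-concept study hands on, would be too favourable. Natural course and expectancy cannot be removed from an uncontrolled design, but this source of misattribution can be.

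**Working it through.** The documents give no effect size, SD or power for the sample of 20, so there is no planned figure to reproduce. The check has two parts.

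**1. Which on-study starts the written rules catch**

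| On-study event | Written rule | Result |
|---|---|---|
| Starts paroxetine or fluoxetine, alone or with olanzapine | Section 10 CYP rule | Discontinued |
| Mood worsens | Sections 3 and 11 | Discontinued (Section 3 leaves it to investigator opinion) |
| Unimproved, not worsening, starts an antidepressant or antipsychotic outside the CYP group | None; physician judgment on safety | May stay; scores counted |
| Starts a mood stabiliser outside the CYP group | None, and none at entry | May stay; scores counted |

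The third row is the gap. The full CYP list is attached to the IRB application and is not in the document. I assume that quetiapine and lurasidone are not on it.

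**2. Size**

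From the documents: n = 20 (Section 3); entry MADRS at least 25 (Section 6); response is a fall of at least 50% and remission a MADRS of 10 or less (Section 14). Assumed: an add-on gain of 4, 8 or 12 MADRS points, and an SD of change of 8 to 10.

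*Rates.* One participant is 1/20 = 5 percentage points. The shift is zero if the participant would have responded anyway, or falls short even with the add-on. The fall needed for response is half the baseline, rounded up; subtracting the gain leaves the smallest fall the participant must already have had:

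| Baseline | Fall needed | Own fall, gain 12 | Own fall, gain 8 | Own fall, gain 4 |
|---|---|---|---|---|
| 25 | 13 | 1 | 5 | 9 |
| 30 | 15 | 3 | 7 | 11 |
| 35 | 18 | 6 | 10 | 14 |

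So only someone already partly improved is converted. Remission is harder: the falls needed are 15, 20 and 25.

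*Mean change.* The shift per affected participant is gain/20: 4/20 = 0.2, 8/20 = 0.4, 12/20 = 0.6.

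*Against sampling error.* SE = SD/√20: 8/√20 = 1.79 and 10/√20 = 2.24. The number needed to shift the mean by one SE runs from 1.79/0.6 = 3.0 to 2.24/0.2 = 11.2, about 3 to 11. At a gain of 4 alone it is 1.79/0.2 = 8.9 to 2.24/0.2 = 11.2.

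*Primary test.* As a simple stand-in for the planned time effect, take a paired test of baseline to week 8. Suppose 18 participants improve by 12 points and 2 by 4. The mean is (18×12 + 2×4)/20 = 11.2, and t = 11.2/2.24 = 5.0 to 11.2/1.79 = 6.3. If those two each gain 10 from an add-on, the mean is (18×12 + 2×14)/20 = 12.2 and t = 5.5 to 6.8. The critical value on 19 degrees of freedom is 2.09, so both are far beyond it.

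*Dropping people is not a remedy.* Removing the two altogether gives (18×12)/18 = 12.0, still 0.8 above 11.2.

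**The case against.** **The event may be rare.** At the week 1, 2, 3 and 6 visits, "Subjects will meet with the psychiatrist for weekly assessment and vitals will be collected"; weeks 4 and 8 also include a psychiatric evaluation. Section 11 says "all participants will receive care for mood symptoms". Non-response already has a remedy: "If response in weeks 3-6, defined as a 50% reduction in the MADRS, has not been achieved, and the current dose is well tolerated", the dose goes up, to at most 4 mg/day. Starting an outside drug on top of that within eight weeks may be uncommon. This stands, and it limits the point.

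**Section 11 may already cover it.** The interaction statement lists several tools, including the entry exclusions and dose adjustment, and does not promise a stopping rule for every drug. Physician judgment can also remove someone who adds an antipsychotic. Both are true. But managing interactions is not the same as attributing benefit, and a participant doing well on an add-on would pass a safety test. That is the case that biases the results.

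**Counting every score is a legitimate choice.** It is, if stated. Section 14 calls its analysis set intent-to-treat, but defines only who is included, not which scores count after an added drug. Counting all of them would also describe brexpiprazole plus whatever was added, not the drug the Primary Aim asks about.

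**The shift is within noise.** At n = 20 a 50% rate has a standard error of √(0.5×0.5/20) = 11 percentage points, so one participant's 5 points is less than half of it. That is correct. But this error runs in one direction and costs little to prevent.

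**Conclusion.** The point holds, at modest size. The entry bar is not extended on study, and Section 14 would count the scores of a participant who adds an antidepressant or antipsychotic outside the CYP group. Each such participant shifts the response or remission rate by 0 to 5 percentage points and the mean MADRS change by about 0.2 to 0.6 points; it takes about 3 to 11 of them to shift the mean by one standard error. The gains and SDs are assumptions. The frequency is not in the documents and is probably low.

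Three stronger readings do not follow:

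- **That add-on antidepressants and antipsychotics are freely allowed.** The CYP rule, discontinuation for worsening mood and physician judgment each remove some of these participants.
- **That the primary result is at risk.** In the illustration the time effect is far beyond its critical value with or without the add-on. What is exposed is the estimates.
- **That the repeated-measures ANCOVA must be replaced.** How incomplete series are handled is a separate missing-data question. The protection of the response and remission rates does not depend on it.

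**What to change.** 1. **Protocol, Sections 7 and 10.** State that the bar on non-study antidepressants and antipsychotics applies through week 8. Handle a start as Section 10 handles CYP drugs: discontinuation with aftercare referral and no delay to needed care.
2. **Section 14.** Count anyone who starts such a drug as a non-responder and non-remitter from that date, including those discontinued for it. Exclude MADRS and IDS-SR scores after the start and keep earlier ones. This is needed alongside item 1 because a start may come to light only at a later visit, after scores have been taken.
3. **Reporting.** Give the number of these starts, and of new mood-stabiliser starts, from the medication reports that Section 10 already requires. Mood stabilisers are not barred at entry and may be started for reasons other than depression, so handle those starts only in a sensitivity analysis.

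The cost is a few sentences, with no new visits or participants. The downside is slightly lower response and remission rates if starts occur, and possibly a few extra discontinuations. If none occur, the results are unchanged and the report can say so.

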All data related to the participant's participation in this study will be given a study ID which cannot be traced back to the patient except by study staff. All personal information which can identify the patient's identity will be kept separately from study documents and assessments. All clinical assessments will be collected in paper form and scores transferred to a computer database maintained on a password protected computer, on a secure server behind a firewall. The paper forms will be kept in binders marked only with the patient's study ID and will be kept in a locked room for the required time period following the completion of this study.

A Certificate of Confidentiality will be obtained for this study.

13. Potential Benefits:

This is a non-randomized open-label clinical trial, thus all participants will receive study medication. All participants may personally benefit from the study by experiencing a significant reduction in symptoms of depression associated with bipolar disorder. The researchers hope the information learned from this study will benefit others with bipolar depression in the future. Information gained from this research could lead to better treatment of patients with bipolar depression.

14. Biostatistics:

Primary Aim: Determine if brexpiprazole is associated with a reduction in depressive symptom severity in outpatients with bipolar disorder, depressed mood state.

1) The MADRS will be the primary outcome measure with the IDS-SR as a secondary outcome measure. Weekly scores on the MADRS and IDS-SR will be assessed using one-way repeated measures. Analysis of Covariance (rm-ANCOVA), controlling for age and sex as potential confounding variables, with time as the main effect. Participants will be included if they complete one post-baseline assessment (intent-to-treat sample). In addition, rates of depression response ($\geq 50\%$ reduction from baseline) and remission (≤ 10 on the MADRS and ≤ 12 on the IDS-SR) will be assessed. A significance level of 0.05 will be set for all analyses, with all tests being two-tailed.

Secondary Aims:

- 2) Assess manic symptoms in patients with bipolar disorder receiving brexpiprazole. YMRS scores will be assessed as with the primary aim above.
- 3) Assess cognition in patients with bipolar disorder receiving brexpiprazole. Scores on the RAVLT, Stroop and TMT will be assessed at baseline compared to weeks 4 and 8 separately using paired t-tests or paired-sample Wilcoxon Signed Rank test.

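### The primary rm-ANCOVA has no estimation method or missing-data rule; in its classical form it would drop incomplete patients and so not analyse the stated intent-to-treat sample

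*Combined protocol and SAP*

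**What the plan says.** Section 14 (Biostatistics, Primary Aim) makes the MADRS the primary outcome. The method is given in two fragments: "Weekly scores on the MADRS and IDS-SR will be assessed using one-way repeated measures" and "Analysis of Covariance (rm-ANCOVA), controlling for age and sex as potential confounding variables, with time as the main effect". The analysis set follows: "Participants will be included if they complete one post-baseline assessment (intent-to-treat sample".

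Section 4 schedules MADRS ratings at baseline and at Weeks 1, 2, 3, 4, 6 and 8. Section 14 reuses the primary method for YMRS and for the safety scales (SAFTEE, C-SSRS, AIMS, BAS, SAS). It also asks for response and remission rates.

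The document contains no estimation method (least squares or likelihood), covariance structure, sphericity rule, imputation rule or missing-data sensitivity analysis.

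Early exit is foreseen. Section 3 lists "worsening in mood symptoms, that in the opinion of the investigators requires discontinuation" among the reasons for discontinuation. Section 11 says: "If participants have a worsening of mood symptoms, such as active suicidal ideation, study participation will be discontinued". Pregnancy, serious medical illness and starting an interacting drug are further reasons (sections 3 and 10). Nothing provides for rating a patient after discontinuation.

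**The concern.** The sample rule and the named method pull apart. A patient with only a baseline and a Week 1 rating is in the sample by rule. If the rm-ANCOVA is run in classical form, that patient leaves the analysis, because the method needs a full set of ratings. The primary result would then be a complete-case result labelled intent-to-treat.

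Some losses can be linked to poor outcome, because worsening mood is a reason to discontinue. Patients who stay would then look better than those who started, and improvement would tend to be overstated. Because the wording carries over to the safety scales, scores from early leavers could also go unused.

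**Working it through.** **Inputs from the documents.** N = 20, single arm (sections 1 and 3). Six post-baseline MADRS ratings (section 4). Two-sided 0.05 (section 14), so 2.5% in the direction of improvement. No power calculation, expected change, SD or dropout rate is given, so there is no stated figure to reproduce. Everything below about missingness and variability is assumed.

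**Step 1: sample rule against method.** The rule needs one post-baseline rating. Classical rm-ANCOVA on this schedule needs 7 of 7 ratings (baseline plus six). A patient with baseline and Week 1 has 2 of 7: included by the first, excluded by the second.

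**Step 2: how many are complete.** If each post-baseline rating is missed independently with probability p, expected completers = 20 × (1 − p)^6:

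- p = 0.02: 20 × 0.886 = 17.7
- p = 0.05: 20 × 0.735 = 14.7
- p = 0.10: 20 × 0.531 = 10.6

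If the only loss is dropout after Week 1 at 10%, 20% or 30%, then 18, 16 or 14 are complete. The chance that at least one of 20 is excluded is 1 − 0.9^20 = 88%, 1 − 0.8^20 = 99%, or 1 − 0.7^20 > 99%.

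**Step 3: outcome-linked dropout.** Simulated rating = patient level (SD 5) + individual change (SD 6 or 9) × f(t) + residual (SD 4), at Weeks 0, 1, 2, 3, 4, 6 and 8. The course f(t) is t/8 or an early plateau, (1 − exp(−t/3))/(1 − exp(−8/3)). Dropout is decided after Weeks 1, 2, 3, 4 and 6 from the observed change from baseline, with a 2% chance of leaving when the trigger is not met. Each cell has 20,000 trials of 20 patients. The test is Week 8 minus baseline in completers. Ranges cover both SDs and both courses.

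| Assumed dropout | True change | Complete | Completer mean | Week 8 test shows improvement |
|---|---|---|---|---|
| 8 or more points above baseline: 30% leave | 0 | 75-80% | -1.1 to -2.4 | 7-14% |
| 8 or more points above: 50% leave | 0 | 68-74% | -1.7 to -3.6 | 12-26% |
| 4 or more points above: 50% leave | 0 | 52-54% | -3.2 to -5.6 | 26-48% |
| 5% per visit, unrelated to outcome | 0 | 0.95^5 = 77% | no bias | 2-3% |
| All outcome-linked triggers (8 points at 30-100%, 4 points at 30-50%) | -8 | 67-87% | -8.4 to -11.0 | at least 92% |

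Section 14 tests the overall time effect and sets no Week 8 contrast. Applied to completers at a true change of 0, the time test gives p < 0.05 with a lower Week 8 mean in 7-57% of trials uncorrected, or 4-41% with Greenhouse-Geisser, across all triggers. With unrelated dropout the figures are 3-4% and about 2%.

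**Step 4: does the unwritten choice matter?** A separate illustration used a starting mean of 30 (SD 3.5), a slope of -1.25 per week (SD 0.9) and residual SD 4. The logit of the chance of leaving after a visit was −3.3 + 0.2 × (observed change + 3). The true Week 8 change was -10.0 and 24% left. Complete cases gave -11.5 and last observation carried forward gave -8.1. In a 3,000-patient run of the same set-up, a mixed model gave -9.9, against -9.9 with full data and -11.6 in complete cases.

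**The case against.** **The classical form is never stated.** A reader might infer that the plan commits to a complete-case analysis. It does not: listwise deletion appears nowhere, and the inclusion rule suggests that incomplete series were meant to count. If a mixed model or carrying forward was intended, the conflict disappears. This stands, and it keeps the point conditional. But neither is written, and Step 4 shows that the permitted readings give different answers.

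**The simulated withdrawals are looser than the documents.** Section 3 leaves withdrawal for worsening to the investigators' opinion. Section 11 gives active suicidal ideation as its example and does not require discontinuation for recurrent thoughts without intent to act. Non-response is answered by the titration rule ("If response in weeks 3-6, defined as a 50% reduction in the MADRS, has not been achieved"), not by withdrawal. With residual SD 4, the difference of two ratings has SD 4 × √2 = 5.66. A patient with no real change therefore shows +4 or more at a given visit with probability 1 − Φ(0.71) = 24%, and +8 or more with probability 1 − Φ(1.41) = 8%. The stronger triggers thus count measurement noise as clinical withdrawal, and the mild one does so to a lesser degree. A reader might take 26-48% as the expected error; the documents do not support that. Only the mild trigger is carried into the conclusion.

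**The consequence is limited.** In a 20-patient uncontrolled study, spontaneous change cannot be separated from drug effect in any case. That stands, though completer bias would add to it in the same direction.

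**The analysis baseline.** Because MADRS is rated at both Baseline 1 and Baseline 2, a reader might infer that the baseline is left open. This is largely answered. Section 4 starts the drug at Baseline 2, the study medication text calls that start week 0 or baseline, and eligibility uses the same visit ("MADRS score ≥ 25 at baseline 2 visit"). Section 14 needs only a confirming sentence.

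**Conclusion.** The omission is certain from the text; its effect is conditional. The plan names a method which, in classical form, does not analyse the sample that the plan defines, and it gives no rule to resolve this. The loss of patients could be modest or substantial: 17.7 to 10.6 of 20 complete at assumed miss rates of 2% to 10% per visit.

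Under the mild assumed trigger and no true change, completers show -1.1 to -2.4 points, and a Week 8 test falsely shows improvement in 7-14% of trials against a nominal 2.5%. Stronger assumed triggers give more. If dropout is unrelated to outcome there is no bias. If the true change is about -8, mainly the estimated size is affected. The point therefore matters most if the true improvement is small or absent. It should be settled before the data are analysed.

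**What to change.** Replace the rm-ANCOVA wording in section 14 with a REML linear mixed model on every observed MADRS rating from the stated sample:

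- visit as a category, baseline kept as a response, age and sex as covariates;
- a prespecified covariance that is estimable at n = 20, for example random intercept plus random slope over weeks, and not compound symmetry alone;
- small-sample degrees of freedom, for example Kenward-Roger;
- the overall time test kept, with Week 8 minus baseline and its 95% CI added;
- one sentence confirming that baseline is Baseline 2 (week 0).

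Use the same model for IDS-SR and YMRS, and all observed scores for the safety scales. For response and remission, count patients without a Week 8 rating as non-responders and non-remitters, with an observed-case check. A sensitivity analysis that shifts imputed values for patients withdrawn for worsening is optional; at n = 20 it would rest on very few patients.

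The cost is SAP wording and a different software procedure; no new data or patients are needed. There are three downsides. The model assumes that dropout depends on observed ratings and that the chosen covariance is adequate. It remains biased if patients leave before their worsening is rated. It may also detect a true effect less often than the inflated completer test: in simulation with SD of change 9, it found a true -8 in 63-86% of trials, against at least 92% for completers.
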